4.4 Concomitant Therapy

During the study, participants will be under stable follow-up for a primary brain tumour. Consequently all will have completed primary radiotherapy and/or chemotherapy. Some may continue on routine medications to manage symptoms such as anti-epileptic drugs. Medications and doses will be recorded observationally for clinico-demographic use. No medication will be prescribed or tested as part of this study.

5. SAFETY MONITORING

This is not a trial of a pharmacological compound. We anticipate that the risk of any untoward physical incident as a result of the interventions delivered here is either low, or nil. However brain tumour patients are medically ill, so for completeness and transparency of governance we include the following section. Arguably it is also important because the Health Coaching Intervention is not wholly sedentary: one of the components involves attaining a goal for number of steps taken per day (measured automatically by fitbit-style monitor).

5.1 Definitions

Adverse Event (AE): An adverse event (AE) is any untoward medical occurrence in a study participant which does not necessarily have a causal relationship with the study treatments or procedures. An adverse event can therefore be any unfavourable and unintended sign (including an abnormal laboratory finding), symptom, or disease temporally associated with a treatment or procedure, whether or not considered related.

Adverse Reaction (AR): All noxious and unintended responses related to a study treatment or procedure should be considered adverse reactions.

Serious Adverse Event (SAE): Defined as any untoward medical occurrence in a participant that:

- a) Results in death;
- b) Is life-threatening;
- c) Requires hospitalisation or prolongation of existing hospitalisation;
- d) Results in persistent or significant disability or incapacity, or;
- e) Is otherwise considered medically significant by the Investigator

Important medical events may also be considered serious if they jeopardise the subject or require an intervention to prevent one of the above consequences.

The term "life-threatening" refers to an event in which the participant was at risk of death at the time of the event; it does not refer to an event which hypothetically might have caused death if it were more severe.

Hospitalisations planned prior to enrolment in the trial or for social reasons will not be considered as SAEs. Treatment in an A&E department of less than 24 hours or on an out-patient basis that does not meet any other serious criteria should not be considered as an SAE.

5.2 Expected events

This section lists those events that are to be regarded as expected for reporting purposes. Note that all are common or potentially common events in patients with a primary brain tumour under normal circumstances.

- Fatigue due to tumour or tumour progression
- Epileptic seizures in a patient with epilepsy, or due to tumour progression
- Functional physical deterioration due to tumour or tumour progression
- Psychological distress due to tumour or tumour progression
- Worsening cognitive impairment due to tumour, tumour progression, or late-delayed radiation reaction
- Tumour progression per se
- Death (due to a complication of tumour)
- Late-delayed radiation reaction
- Pulmonary embolus
- Falls and injury secondary to falls

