5.4 Recording and Reporting of Serious Adverse Events

Contact Details for Reporting SAEs

SCTRU [contact] (preferred method)
SCTRU [contact] (Mon – Fri 9am-4pm)

All serious adverse events that occur after the signing of written informed consent and within 30 days after the final study procedure will be recorded on the SAE report form. In addition, any SAE that occurs more than 30 after final study procedure and is deemed to be related to a study procedure should be recorded on the SAE report form. The SAE report form must be signed by the Principal Investigator of the centre involved and faxed to SCTRU within 24 hours of the Investigator first becoming aware of the event. All initial SAE reports should contain the following minimum information:

- Reporter details
- At least one suspect procedure
- At least one subject identifier (trial number/patient initials)
- Adverse Event term
- Causality assessment

A fax receipt will be sent to the relevant centre by SCTRU to acknowledge receipt of the SAE report form, and SCTRU will notify the Chief Investigator (CI) The sponsor will be notified of all SAE's which occur in the form of a line listing which will be sent to them by SCTRU every 2 months. Any SAE that has been assessed as related will be forwarded to the CI by SCTRU. Any SAE that is deemed to be both **related** (ie resulted from administration of any of the research procedures) and **unexpected** (ie not listed in the protocol as an expected occurrence) will be notified to the Research Ethics Committees within 15 days of the CI becoming aware of the event

Related and unexpected SAE's should be reported to the REC using the 'Non-CTIMP safety report to REC form'. This should be signed by the CI and include a statement on the assessment of the implications, if any, for the safety of study participants and how will these be addressed. The coordinator of the REC should acknowledge receipt of the safety report within 30 days. The MHRA do not require to be notified of SAEs within this trial, as the study does not involve the use of an investigational medicinal product. http://www.hra.nhs.uk/resources/during-and-after-your-study/progress-and-safety-reporting/. SCTRU will notify the PI's at all of the participating centres of the occurrence of any related and unexpected SAE's

There is no requirement to submit annual safety reports to the REC in addition to the information provided through the annual progress report.

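### Section 5.2 lists falls as expected whatever their cause, so a serious fall judged related to Health Coaching would trigger neither the 15-day ethics committee report nor the notice to all centres

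*Protocol*

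**What the plan says.** Section 5.2 opens by stating its function: "This section lists those events that are to be regarded as expected for reporting purposes". It gives the basis for the list as background frequency in the disease: "Note that all are common or potentially common events in patients with a primary brain tumour under normal circumstances". Ten entries follow. Most carry a cause, for example "Functional physical deterioration due to tumour or tumour progression". Even death is qualified; the entry begins "Death (due to a complication of tumour". The last entry is "Falls and injury secondary to falls", with no qualifier.

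Section 5.4 makes that list decisive. For serious events that are both related and unexpected, it explains the second term and states the consequence in one run: "ie not listed in the protocol as an expected occurrence) will be notified to the Research Ethics Committees within 15 days". The same two-part condition governs notice to the sites: "SCTRU will notify the PI's at all of the participating centres of the occurrence of any related and unexpected SAE's".

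Section 5 puts the physical risk of the interventions at low or nil. It includes safety reporting first because these patients are medically ill. It then adds, in hedged terms, that "the Health Coaching Intervention is not wholly sedentary", and points to the step goal. Section 4 (Arm 2) describes further physical components: muscle activation exercises and a target of three 30-minute exercise sessions a week. Arm 3 receives the same coaching.

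**The concern.** An expectedness list usually sorts events that the disease would produce anyway from events that may say something new about the intervention. Limiting an entry by cause does that job. The falls entry has no such limit, yet a fall is an event that exercise sessions or a step goal could plausibly bring about.

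If an investigator judged a serious fall to be caused by Health Coaching, the list would still class it as expected. The REC would receive no expedited report, and investigators at the other two centres, where the same coaching is being delivered, would not be told under the rule that exists for that purpose. At stake is the speed with which a related harm becomes known outside the centre where it happened. The primary feasibility outcome, the analysis and the recording of events are not affected.

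**Working it through.** The plan states no figure to reproduce. The check applies the section 5.4 rule to the section 5.2 list.

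**Step 1. Sort the ten entries of section 5.2 by how they are limited.**

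| Type of entry | Entries | Count |
|---|---|---|
| Limited wholly by cause (tumour, progression or late radiation effect) | fatigue; physical deterioration; psychological distress; cognitive worsening; death | 5 |
| Names the disease or earlier treatment itself | tumour progression; late radiation reaction | 2 |
| Partly open | seizures (expected in any patient with epilepsy, or if due to progression) | 1 |
| No limit on cause | pulmonary embolus; falls and fall injuries | 2 |

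5 + 2 + 1 + 2 = 10. Seven of the ten cannot cover an event caused by coaching. Falls are one of three entries that can, in whole or in part.

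**Step 2. Apply the rule to a serious fall judged related to Health Coaching.**

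- Serious under section 5.1 (for example, it requires hospital admission): yes.
- Related: yes, by premise.
- Unexpected, meaning not listed: no, because falls are listed without restriction.
- Related and unexpected: false. Neither the 15-day REC notification nor the notice to all principal investigators applies.

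The sentence about events being common in the disease explains why the list was drawn up. It does not narrow the entry, because section 5.4 asks only whether the event is listed.

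**Step 3. Repeat with the entry limited by cause.** A fall judged related to coaching is then unlisted, hence unexpected, and both notices apply. A serious fall judged unrelated still fails the first half of the test and generates no notice, whether listed or not. The only added reports are serious falls judged related.

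**Step 4. List the routes that remain under the present wording.**

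- Serious adverse event form, signed by the site's principal investigator and including a causality assessment, to the trials unit within 24 hours of awareness (5.4).
- Chief investigator, notified by the trials unit, with related events forwarded (5.4).
- Sponsor, by line listing every two months (5.4).
- Data monitoring committee: six-monthly at first, an extra meeting after 13 patients, and others at its discretion (9.2). Its remit covers adverse events and tolerability of Health Coaching (11).
- Steering committee, whose remit includes patient safety (9.3), and a management group that meets quarterly (11).
- REC: only what the annual progress report carries (5.4).

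None of these is stated to inform the REC or the other centres' investigators promptly. The scheduled six-month interval of the monitoring committee is 6 × 52/12 = 26 weeks, longer than one participant's 16-week follow-up.

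**Step 5. Exposure.** Arms 2 and 3 receive Health Coaching: 20 + 20 = 40 of 60 planned participants, or two thirds. This counts people offered the activity components. It is not a count of expected falls.

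**The case against.** The strongest reply is that falls are foreseeable in this population, so listing them is a legitimate choice, and that much oversight remains. Both halves have force. Background falls should stay expected, and the routes in Step 4 mean that a related serious fall would be known to the trials unit and the chief investigator quickly. A reader might infer from the listing that such a fall escapes scrutiny; the documents do not support that.

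Other stronger readings also fail:

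- *That activity is the reason the protocol has a safety section.* Section 5 gives it as a second, hedged reason, after the patients' medical illness.
- *That falls are a lone anomaly.* Pulmonary embolus is equally open, and so is the part of the seizure entry that covers patients with epilepsy.
- *That coaching is shown to cause falls, or that falls are its leading harm.* The protocol gives no fall rate and no ranking of harms. The link to exercise and step goals is a judgement of plausibility.
- *That every serious event related to either intervention should be treated as unexpected.* That would remove the second half of the section 5.4 test and leave the section 5.2 list almost without function. It is not needed to close this gap.

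What the reply does not answer is the narrow point. Foreseeability in the disease is no reason to class as expected a fall that the investigator attributes to the intervention, and no remaining route replaces the two notices.

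**Conclusion.** The point holds in a limited form. As sections 5.2 and 5.4 stand together, a serious fall judged related to the activity components of Health Coaching would trigger neither the 15-day REC report nor the notice to all centres. This follows from the wording and needs no numerical assumption; it rests only on the investigator having judged the fall related. How often that would happen cannot be estimated from the protocol, and may be never in a trial of 60. The loss is expedited notice to the REC and across sites, not oversight as a whole. It is a modest gap in safety reporting that is worth closing because closing it is cheap.

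**What to change.** In section 5.2, limit the falls entry by cause in the way its neighbours are limited, for example: *falls, and injury from falls, due to tumour, tumour progression or its treatment*. It should be plain that treatment here means treatment of the tumour and not a study intervention, so that a fall judged related to Health Coaching counts as unexpected under section 5.4. Section 5.4 itself needs no change.

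The cost is one phrase in a protocol amendment and possibly a few additional expedited reports, confined to serious falls judged related. Patient care, data collection and analysis are unchanged. If the sponsor prefers to keep the entry open, the protocol should say that the breadth is intended.

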5.3 Recording of Adverse Events

All adverse events occurring after signing of informed consent through to 30 days after final study procedure will be recorded in the subject's notes and transcribed to the CRF.

Any medical conditions or diseases present prior to signing of informed consent should only be considered an adverse event if there is a worsening of the condition.

5.4 Recording and Reporting of Serious Adverse Events

Contact Details for Reporting SAEs

SCTRU [contact] (preferred method)
SCTRU [contact] (Mon – Fri 9am-4pm)

All serious adverse events that occur after the signing of written informed consent and within 30 days after the final study procedure will be recorded on the SAE report form. In addition, any SAE that occurs more than 30 after final study procedure and is deemed to be related to a study procedure should be recorded on the SAE report form. The SAE report form must be signed by the Principal Investigator of the centre involved and faxed to SCTRU within 24 hours of the Investigator first becoming aware of the event. All initial SAE reports should contain the following minimum information:

- Reporter details
- At least one suspect procedure
- At least one subject identifier (trial number/patient initials)
- Adverse Event term
- Causality assessment

A fax receipt will be sent to the relevant centre by SCTRU to acknowledge receipt of the SAE report form, and SCTRU will notify the Chief Investigator (CI) The sponsor will be notified of all SAE's which occur in the form of a line listing which will be sent to them by SCTRU every 2 months. Any SAE that has been assessed as related will be forwarded to the CI by SCTRU. Any SAE that is deemed to be both **related** (ie resulted from administration of any of the research procedures) and **unexpected** (ie not listed in the protocol as an expected occurrence) will be notified to the Research Ethics Committees within 15 days of the CI becoming aware of the event

Related and unexpected SAE's should be reported to the REC using the 'Non-CTIMP safety report to REC form'. This should be signed by the CI and include a statement on the assessment of the implications, if any, for the safety of study participants and how will these be addressed. The coordinator of the REC should acknowledge receipt of the safety report within 30 days. The MHRA do not require to be notified of SAEs within this trial, as the study does not involve the use of an investigational medicinal product. http://www.hra.nhs.uk/resources/during-and-after-your-study/progress-and-safety-reporting/. SCTRU will notify the PI's at all of the participating centres of the occurrence of any related and unexpected SAE's

There is no requirement to submit annual safety reports to the REC in addition to the information provided through the annual progress report.

5.5 Pregnancies

Any pregnancy in a trial participant that occurs during study participation should be reported to SCTRU within 24 hours of the site RA or PI becoming aware of its occurrence, using the contact details in Section 5.3. The SCTRU will ensure that the information is passed to the relevant Health Coach to make them aware.

6. DATA MANAGEMENT

All data will be handled, computerised and stored in accordance with the Data Protection Act 1998 and NHS National Services Scotland Confidentiality Guidelines.

6.1 Data Collection

Health coaching:

At the first health coaching session, participants will be given a home diary to record their progress. The health coach will initiate a secure end-to-end NHS.net-based email thread, by emailing the participant's preferred email address from an nhs.net account, with their study code number and "[Secure]" in the subject line. All study email communication between the health coach and the participant will use this encrypted Study Thread. At intervals by agreement, the participant will take a clear picture of their completed home diary on their smartphone. They will access their email account and email the health coach on the secure Study Thread, attaching the picture of their diary. In this way the health coach will gather data securely, with minimal effort for participants and without the need for a thirdparty app or the posting of hard copies of the diary. Follow-up appointments will be guided by these securely-emailed images of the participant's home diary. After the appointment the health coach will forward the diary image via nhs.net to the RA/RN for data entry.

Alternatively, participants may choose to attend follow-up in person. In this case they will simply be asked to bring their diary with them to the appointment. The health coach will use the diary to guide the appointment. At the end of the appointment the health coach will scan the diary and save the image file on an NHS Lothian-encrypted memory stick. They will then use nhs.net to email the image file to the RA/RN for data entry. Once acknowledged by the RA/RN, the scanned image file will be deleted from the memory stick.

Patient activation:

The Patient Activation interviews will not be audio-recorded. The coaches will not take written notes during the interview. Immediately after the interview, the patient activation coach will write an email, send to the RA/RNvia nhs.net, summarising the interview. The RA/RNs will upload the text to the central study database.

At site:

Data generated from T0, T1 and T2 interviews will be collected at site, The data will then be checked and validated by SCTRU. The data collected will include:

- initial clinical details at randomisation
- concomitant medications
- adverse events
- survival
- withdrawal
- protocol deviations

6.2 Record Keeping and Archiving

Study documentation will be retained at site until the end of follow up. The documentation will then be archived using an NHS-approved service, according to current legislative requirements.

7. STATISTICS

7.1 Sample Size

60 participants will be randomised to one of three study arms:

- Control (n=20);
- Health Coaching (n=20);
- Health Coaching plus Patient Activation intervention (n=20).

7.2 Power considerations

In line with NIHR guidance²⁵ this study is neither intended nor powered to study the efficacy of Health Coaching. Rather our sample size of 60 patients (20 patients per group) is based on what is reasonably sufficient to study feasibility. Equally the subsample of 24 patients who will receive a qualitative interview is in line with accepted practice in the qualitative research field.

7.3 Exit strategy to a definitive trial

We will develop systems, relationships, and experience in the three centres necessary to running a definitive trial. We will in particular pilot the FACIT-F scale³³ as a possible primary outcome measure, given that it is a frequently used fatigue scale for which validated minimal clinically important differences have been published. We have additionally conducted a power calculation to illustrate the capacity for a definitive trial. Assuming: (1) a standard 2-arm RCT and 1-1 randomisation schedule; (2) a typical standard deviation in the FACIT-F of SD=12; (3) Alpha (p)= 0.05, then in order to have 90% power to detect a minimal clinically important difference in the FACIT-F of 8 points, we would require n=49 participants per arm. The current feasibility study will inform us further about rates of recruitment and attrition, and likely effect sizes. Given the prevalence of fatigue in patients with a brain tumour, and because we will pilot systems over a wide geographical catchment, we see a viable exit strategy from this feasibility study.

7.4 Analysis Plan

Final analysis will be performed at the end of the study, i.e. when all patients have completed their assessments and all data has been cleaned and the database locked.

Statistical quality assurance will be carried out to correct spurious data and to mimimise the level of missing data.

Analysis will be carried out on all patients randomised to the study.

Number of patients recruited over a 12 month period will be tabulated overall by site and treatment arm. This will be compared to the target of 20 patients.

Number and proportion of patients retained within the trial to the T2 endpoint (16 weeks after randomisation) will be tabulated overall and by site and treatment arm. This will be compared to the target that at least 60% of patients will be retained until the T2 endpoint.

The mean change (from baseline to 16 week follow up) in outcome scale scores with 95% confidence intervals will be calculated for each treatment arm.

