Developing systems and piloting outcome measures: In line with MRC guidance²⁴ we will take the opportunity to develop and pilot systems and potential outcome measures for a future definitive trial. We will develop and use a structured clinical interview for fatigue, alongside the Brief Fatigue Inventory³² and the Functional Assessment of Chronic Illness Therapy-Fatigue (FACIT-F)³³, to study the impairment caused by fatigue over time. We will pilot the Psychological Outcome Profiles (PSYCHLOPS) tool³⁴ to track progress towards reducing the impact of fatigue on the most important functional outcomes for study participants.. As regards confounding variables, anxiety and depression will be screened using the Hospital Anxiety and Depression Scale³⁵ while cognitive function will be screened using the Addenbrooke's Cognitive Examination-III (ACE-III).³⁶ We will record prescribed medication at each study time-point. For all these outcomes we will gather pilot data on the magnitude of effect size in the treatment arms versus control, in order to estimate likely effect sizes in a larger trial.

We may in addition pilot instruments to examine the Health Economic costs and potential benefits of these interventions. We will assess health benefits using the EQ-5D which is the nationally-recommended instrument for this specific purpose.³⁷

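### Section 4.1 promises effect sizes versus control, but the stated analysis gives only each arm's own mean change, with no between-arm difference or interval

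*Protocol*

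**What the plan says.** Four places in the protocol bear on this.

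- Section 4.1, on piloting outcome measures, says of all the listed scales, with a later and bigger study in view: "we will gather pilot data on the magnitude of effect size in the treatment arms versus control, in order to estimate likely effect sizes".
- Section 7.3 repeats the aim: "The current feasibility study will inform us further about rates of recruitment and attrition, and likely effect sizes".
- Section 7.4 gives one analysis of the scales, the mean change from baseline to week 16: "in outcome scale scores with 95% confidence intervals will be calculated for each treatment arm". The secondary outcome in section 2.2 and in the Trial Summary is likewise a mean change per arm.
- Section 7.2 states that "this study is neither intended nor powered to study the efficacy of Health Coaching".

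Section 3.2 requires a BFI score of at least 4 out of 10 for randomisation. In the schedule (section 4.2, Figure 2) the BFI is marked at screening, T1 and T2 but not at T0.

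**The concern.** The quantity promised in 4.1 is a contrast with control. The quantity fixed in 2.2 and 7.4 is each arm's own change. An analyst who follows 7.4 will produce three within-arm means with three intervals, and neither a difference versus control nor an interval for one.

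Within-arm change is also a poor stand-in for the contrast. Patients enter because they score high on a fatigue scale, so part of any later fall can be regression to the mean. The randomised control arm shares that drift and a between-arm difference removes it; an arm's own change does not.

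At stake is whether the pilot reports the comparison it says it will, and whether the uncertainty of that comparison is visible to those who plan the next trial. The primary outcome (recruitment and retention) is not touched.

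**Working it through.** **Inputs.** From section 7.3: "a typical standard deviation in the FACIT-F of SD=12", the "minimal clinically important difference in the FACIT-F of 8 points", alpha 0.05, 90% power, and "a standard 2-arm RCT and 1-1 randomisation schedule". From section 7.1: 20 per arm. From section 2.1: attrition of up to 40% in total is tolerated, which leaves 12 of 20 per arm if it falls evenly. The protocol gives no baseline-to-follow-up correlation r, so I assume 0.3 to 0.7. I treat 12 as the SD of scores at one time point.

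**1. The plan's own figure.** n per arm = 2(z₀.₉₇₅ + z₀.₉₀)² SD²/d² = 2 × (1.960 + 1.282)² × 144/64 = 47.3, so 48 by the normal approximation. The two-sample t-test gives 48.26, so 49. The stated 49 per arm reproduces with a two-sided alpha. It rests on the 8-point difference, not on a pilot estimate.

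**2. Precision of an unadjusted difference versus control.** Half-width = t(2n−2) × SD × √(2/n).

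- 20 per arm: SE = 12 × √(2/20) = 3.79; half-width = 2.024 × 3.79 = 7.7 points.
- 12 per arm: SE = 12 × √(2/12) = 4.90; half-width = 2.074 × 4.90 = 10.2 points.

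An observed difference of 8 would have an interval of about 0.3 to 15.7 at 20 per arm and −2.2 to 18.2 at 12 per arm.

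**3. Within-arm intervals are a different quantity.** At r = 0.5 the SD of change is 12 × √(2 × 0.5) = 12. One arm's half-width at n = 20 is then 2.093 × 12/√20 = 5.6 points, against 7.7 for the difference in change between two such arms. Setting separate arm intervals side by side therefore understates the uncertainty of the contrast.

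**4. What baseline adjustment gains.** SD of change = 12√(2(1−r)); ANCOVA residual SD = 12√(1−r²), with 2n−3 degrees of freedom. Half-widths for the between-arm difference, in FACIT-F points:

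| r (assumed) | 12 per arm, change score | 12 per arm, ANCOVA | 20 per arm, change score | 20 per arm, ANCOVA |
|---|---|---|---|---|
| 0.3 | 12.0 | 9.7 | 9.1 | 7.3 |
| 0.5 | 10.2 | 8.8 | 7.7 | 6.7 |
| 0.7 | 7.9 | 7.3 | 6.0 | 5.5 |

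**5. Regression to the mean.** On the selecting scale, a group chosen k SD above the mean is expected to move back by (1−r)k SD on retest. For k = 1 and r from 0.3 to 0.7 that is 0.7 to 0.3 SD with no treatment effect. This applies most directly to the BFI: by Figure 2 its screening score is both the selection value and the only value before randomisation. On the FACIT-F the shift would be k × [corr(BFI, FACIT-F at T0) − corr(BFI, FACIT-F at T2)] SD. The protocol gives neither correlation, so its size there cannot be stated.

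**6. What the pilot can supply better.** If the pooled SD is estimated as 12, its 95% interval, 12√(df/χ²), is about 10.1 to 14.7 with 60 analysed (df 57) and 9.7 to 15.8 with 36 (df 33). For contrast, suppose the true difference is 8 and the estimate falls one SE low or high. Put into the formula of step 1, it would give 172 or 22 per arm from a pilot of 20 per arm, and 315 or 19 from 12 per arm. This shows why a caution is worth writing down; the protocol does not say that it will do this.

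**The case against.** Section 7.4 computes exactly what section 2.2 defines, and it does not forbid a contrast. Model choice is commonly left to a statistical analysis plan, which may exist and may add one. A reader with arm means, intervals and numbers could also rebuild an unadjusted difference by hand. All of this is fair and limits the weight of the point. It does not remove the mismatch: 4.1 names a comparison with control, and the stated outcome and analysis name something else. A baseline-adjusted difference cannot be rebuilt from arm summaries.

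Stronger readings are tempting, and the document does not bear them out.

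- A reader might infer that arm-wise change will be presented as benefit and will overstate it. No section reads it that way, 7.2 disclaims efficacy, and the control arm is reported alongside. Nor is improvement in every arm established: section 5.2 lists fatigue and functional decline from tumour progression as expected events, and selection is on the BFI rather than the FACIT-F.
- A reader might infer that the definitive trial will be sized on the pilot point estimate. Section 7.3 bases its illustration on "90% power to detect a minimal clinically important difference in the FACIT-F of 8 points" and says only that the pilot will inform likely effect sizes. That wording is loose, but it is not a sizing rule.
- A reader might infer that 4.1 contradicts 7.2. Imprecise estimates reported with intervals are compatible with a trial that is not powered for efficacy.

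The 12-per-arm case is also the least favourable one tolerated under even loss. The 40% limit is on total attrition, so a single arm could end above or below 12.

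**Conclusion.** The concern holds as a mismatch inside the protocol. Section 4.1 promises effect size versus control; sections 2.2 and 7.4 provide only within-arm change, with no between-arm estimate or interval. Once reported, the contrast would be imprecise: about ±7.7 FACIT-F points at 20 per arm and ±10.2 at 12 per arm, about as wide as the 8-point target or wider. This rests on the protocol's SD of 12 and, for the second figure, on attrition spread evenly. The gain from adjustment depends on an unknown correlation. Regression to the mean is a plausible part of arm-wise change, chiefly on the BFI, and is unquantified on the FACIT-F.

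The evidence does not support making the contrast the main summary of the scales, or striking every mention of effect sizes: the trial is not powered for efficacy, and an interval can still help to judge whether 8 points is plausible. What is supported is a descriptive contrast with its interval and a caution on its use. The feasibility conclusions and the stated 49 per arm stand.

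**What to change.** **Section 7.4.** Keep the arm-wise means. Beside them add, for each scale, the baseline-adjusted difference at T2 (ANCOVA) with a 95% confidence interval, for Health Coaching versus control and for Health Coaching plus Patient Activation versus control. Label these as descriptive estimation without efficacy testing. For the BFI, name the value used as baseline: Figure 2 offers only the screening score, although section 4.3 could be read as placing every measure at T0.

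**Sections 4.1 and 7.3.** State that the between-arm estimates will be imprecise, giving the half-widths of about 7.7 and 10.2 points and their assumptions. State that the definitive trial's target difference stays on the minimal clinically important difference, and that the pilot mainly supplies the SD, the baseline-to-follow-up correlation, recruitment and attrition.

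**Cost.** Changes of wording and a small amount of extra analysis on data already collected. The downside is a set of wide intervals that could be misread as efficacy results, which is why the label matters.
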